### **7.5 Nivolumab**

Please refer to the Nivolumab Investigator Brochure or Appendix E to the protocol for toxicity management algorithms which include specific treatment guidelines. These algorithms should

be followed unless there are specific clinical circumstances for which the treating physician decides an alternative treatment approach is clinically appropriate. Consultation with the study PI or drug monitor is recommended.

Adverse events associated with Nivolumab exposure may represent an immunologic etiology. These AEs may occur shortly after the first dose or several months after the last dose of treatment. Nivolumab must be withheld for drug-related toxicities and severe or life-threatening AES.

- **Drug will be held for any indication suggestion of cardiac dysfunction of any grade pending evaluation**
- **Drug will be permanently discontinued for treatment related grade 3 or 4 cardiac dysfunction and grade 2 events that do not recover to baseline or that reoccur**
- **Treatment as clinically indicated for cardiomyopathy**

Cardiac *	Management/Next Dose for Nivolumab Cardiac Toxicities
Less than grade 2	Hold dose pending evaluation and observation.** Evaluate for signs and symptoms of CHF, ischemia, arrhythmia or myositis. Obtain history EKG, CK (for concomitant myositis), CK-MB. Repeat troponin, CK and EKG 2-3 days. If troponin and labs normalize without evidence of myocarditis may resume therapy. If labs worsen or symptoms develop then treat as below.
Grade $\geq 2$ with suspected myocarditis	Hold dose. Admit to hospital. Cardiology consult. Rule out MI and other causes of cardiac disease. Cardiac Monitoring. Cardiac Echo. Consider cardiac MRI and cardiac biopsy. Initiate high dose methylprednisolone and immune suppression as clinically indicated. If no improvement within 24 hours consider adding either infliximab, ATG or tacrolimus.. May resume therapy if there is a return to baseline and myocarditis is excluded or considered unlikely.
Grade $\geq 2$ with confirmed myocarditis	Off protocol therapy. Admit to CCU (consider transfer to nearest Cardiac Transplant Unit). Treat as above. Consider high dose methylprednisolone Add ATG or tacrolimus if no improvement. Off protocol treatment.

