Liver Function AST, ALT, Bilirubin	Management/Next Dose for Nivolumab
≤ Grade 1	Hold at investigator discretion until ULN or baseline. Resume at same dose level.
Grade 2	Grade 2 (3X UNL to 5X UNL): Hold until grade 1 (UNL-3X UNL) or baseline. Resume at same dose level at investigator discretion.
Grade 3	Grade 3 (5X UNL to 20X UNL) Hold until grade 1 or baseline. Resume at same dose level at investigator discretion with return to grade 1 or baseline within 7 days without steroids. If persistent or steroids are required, off protocol therapy.
Grade 4	Off protocol therapy.

Continued treatment of active immune mediated hepatitis may exacerbate ongoing inflammation.

Holding drug to evaluate liver function test (LFT) changes and early treatment are recommended. LFT changes may occur during steroid tapers from other events and may occur together with other GI events including cholecystitis/pancreatitis.

Please note: Grades for liver function follow UNL rather than multiples of baseline.

Recommended management: see Hepatic AE management algorithm

Diarrhea/ Colitis	Management/Next Dose for Nivolumab
≤ Grade 1	Hold until baseline. No change in dose.
Grade 2	Hold until baseline. No change in dose.
Grade 3	Resume at same dose level at investigator discretion if resolved to grade 1 within 7 days without steroids and no evidence of colitis. If persistent or steroids are required off protocol therapy.
Grade 4	Off protocol therapy.
See GI AE Algorithm for management of symptomatic colitis.	
Patients with Grade 2 symptoms but normal colonoscopy and biopsies may be retreated after resolution.	
Patients who require systemic steroids should be taken off study treatment.	
Please evaluate pituitary function prior to starting steroids if possible without compromising acute care. Evaluation for all patients for additional causes includes C. diff , acute and self-limited infectious and foodborne illness, ischemic bowel, diverticulitis, and IBD.	
Recommended management: see GI AE management Algorithm	

Pancreatitis Amylase/Lipase	Management/Next Dose for Nivolumab
≤ Grade 1	Continue at same dose level if asymptomatic at investigator discretion.
Grade 2	Continue at same dose level if asymptomatic at investigator discretion. If symptomatic, resume at same dose level when resolved

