# Hepatic Adverse Event Management Algorithm

Rule out non-inflammatory causes. If non-inflammatory cause, treat accordingly and continue I-O therapy. Consider imaging for obstruction.

[figure not shown]
Patients on IV steroids may be switched to an equivalent dose of oral corticosteroids (e.g. prednisone) at start of tapering or earlier, once sustained clinical improvement is observed. Lower bioavailability of oral corticosteroids should be taken into account when switching to the equivalent dose of oral corticosteroids.

\*I-O therapy may be delayed rather than discontinued if AST/ALT  $\leq 8 \times$  ULN and T.bili  $\leq 5 \times$  ULN.

\*\*The recommended starting dose for grade 4 hepatitis is 2 mg/kg/day methylprednisolone IV.

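### Internal inconsistency: after a quickly reversing, steroid-free hepatic event above 8 x ULN (AST/ALT) or 5 x ULN (bilirubin), the Section 7.5 liver table permits nivolumab to resume, but the Appendix E footnote offers no delay option

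*Combined protocol and SAP*

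**What the plan says.** **Section 7.5, liver function table.** One table serves AST, ALT and bilirubin. Its grade 3 row reads "Grade 3 (5X UNL to 20X UNL) Hold until grade 1 or baseline", followed by "Resume at same dose level at investigator discretion with return to grade 1 or baseline within 7 days without steroids" and then "If persistent or steroids are required, off protocol therapy". Grade 4 is off protocol therapy. A note fixes the scale: "Grades for liver function follow UNL rather than multiples of baseline". The table ends with a pointer: "Recommended management: see Hepatic AE management algorithm".

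**Appendix E, hepatic algorithm.** The flowchart is not available, but its surrounding text is. If the cause is non-inflammatory, immuno-oncology therapy continues. A starred footnote says "I-O therapy may be delayed rather than discontinued if AST/ALT" is no more than 8 x ULN and total bilirubin no more than 5 x ULN.

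**Section 7.5, opening paragraph.** The Investigator Brochure or Appendix E algorithms should "be followed unless there are specific clinical circumstances" that lead the treating physician to judge another approach appropriate. Consulting the study PI or drug monitor is recommended.

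**Two further rules reach the same event.** Section 7.1 lets patients restart after a non-hematologic DLT once the event is back to grade 1 or lower, or to baseline. It then sends the reader to Section 7.3 for nivolumab. A bullet in Section 7.5, under the table for all other events, says that certain grade 3 or 4 laboratory abnormalities do not require discontinuation, including those that need no treatment.

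**The concern.** Restarting a checkpoint inhibitor after a marked rise in liver tests is a safety decision, and the table's own note warns that continued treatment during active immune-mediated hepatitis may worsen it. An investigator who reads the table may restart nivolumab. One who reads the footnote finds that the condition for delaying rather than discontinuing has not been met. Both are following the current protocol.

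The difference can fall inside the DLT window, which runs from cycle 1 day 15 to the end of cycle 3. One patient could go on receiving nivolumab through that window while another with the same laboratory course stops. Dose levels hold 3 to 6 patients, so a single discordant case is a visible share of a cohort. Section 9.1 replaces patients who do not finish the window for reasons other than DLT. Stopping nivolumab after an event that is not itself a DLT could therefore also raise the question of whether that patient must be replaced.

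**Working it through.** No sample size, power or error rate is involved. The check is a comparison of two sets of limits, both in multiples of ULN and so directly comparable.

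**Inputs**
- Table (Section 7.5): grade 3 is 5 to 20 x ULN. Resumption needs recovery to grade 1 or baseline within 7 days, no steroids, and the investigator's agreement.
- Footnote (Appendix E): delay is available if AST/ALT ≤ 8 x ULN **and** bilirubin ≤ 5 x ULN. The two conditions are joined by *and*, so the delay option is lost when AST/ALT > 8 **or** bilirubin > 5.

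**Cases, for an event not attributed to a non-inflammatory cause**

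| Peak values and course | Section 7.5 table | Appendix E footnote | Conflict? |
|---|---|---|---|
| AST/ALT 5–8, bilirubin ≤ 5; recovers within 7 days, no steroids | Resumption allowed | Delay allowed | No |
| AST/ALT > 8 to 20, or bilirubin > 5 to 20; recovers within 7 days, no steroids | Resumption allowed | No delay option; discontinuation implied | **Yes** |
| Same values; persistent, or steroids needed | Off protocol therapy | No delay option | No |
| Any value > 20 | Off protocol therapy (grade 4) | No delay option | No |

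**Illustration.** ALT peaks at 10 x ULN with normal bilirubin, and is back to grade 1 on day 4 without steroids.
- Table: 5 < 10 ≤ 20 and 4 ≤ 7, so resumption is allowed.
- Footnote: 10 > 8, so the delay option does not apply.
- DLT status: Section 6.3 exempts AST, ALT or alkaline phosphatase rises that resolve to below grade 2 within 5 days without steroids. Here 4 ≤ 5, so this event is not a DLT and the patient is still under observation when the two texts part.

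**Does another passage settle it?**
- The opening of Section 7.5 makes the algorithms the default and allows exceptions in particular clinical circumstances. The table is not such an exception: it is a general rule printed in the same section.
- The table's pointer to the hepatic algorithm gives no order of precedence.
- Section 7.1 applies if the event is a DLT, for example a drug-related ALT rise that takes 6 or 7 days to settle. Its restart condition carries neither the 7-day limit nor the no-steroid limit. Its pointer for nivolumab leads to Section 7.3, which in the body of the protocol deals with missed decitabine and venetoclax doses. Nivolumab is in Section 7.5; the table of contents still lists it as 7.3.
- The laboratory-abnormality bullet could be read to cover a self-limiting transaminase rise. It sits under a different table, so its reach is unclear.

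None of these says whether the liver table or the footnote governs.

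**The case against.** The strongest reply is that the Appendix E side rests on a footnote whose flowchart cannot be read here. The sentence is permissive, and the box it belongs to may carry its own conditions on grade, duration or steroid use. That stands as a limit: discontinuation above 8 x or 5 x ULN is the natural reading of an option to delay rather than discontinue, but it remains an inference until the figure is checked.

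A reader might infer that re-challenge after any severe hepatitis depends on which page is open. The documents do not support that. The table's permission is discretionary and needs recovery within 7 days without steroids; outside those conditions both texts stop nivolumab. Appendix E also continues therapy for a non-inflammatory cause, whatever the values.

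A reader might also gauge the problem by how much of the 5 to 20 x ULN band lies above the footnote's limits. That measures a scale, not patients. The documents give no frequency for events meeting all the conditions, so no proportion of patients can be stated.

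It is also fair to say that the dose-escalation consequence is modest. Nivolumab is a flat 240 mg at every dose level, and the levels differ only in venetoclax days. Whether the hepatic event itself is a DLT is decided by Section 6.3, not by later resumption. The DLT count for that event is the same under either reading.

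Finally, the default-with-exceptions wording and the recommended consultation soften the conflict. They do not remove it, because both texts are written as general rules for the same values.

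**Conclusion.** The inconsistency is real and narrow. It applies to hepatic events not attributed to a non-inflammatory cause, with AST/ALT above 8 and up to 20 x ULN or bilirubin above 5 and up to 20 x ULN, that reverse within 7 days without steroids. For these the table permits nivolumab to resume at the investigator's discretion, while the footnote does not offer delay.

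Two assumptions carry this. The first is that the missing flowchart adds nothing that changes the footnote's meaning. The second is that the single printed grade 3 band applies to bilirubin as well as to transaminases. The table's title says so, and the protocol prints no separate bilirubin limits, although it grades toxicity by CTCAE version 5.0.

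The possible effects are uneven handling of a safety decision across sites and an occasional replacement question. There is no effect on sample size or on the 13-of-30 response rule. It should be corrected because it concerns re-exposure after liver toxicity and the correction is cheap.

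**What to change.** 1. Check the hepatic flowchart, then reconcile the Section 7.5 liver table with the Appendix E footnote into one rule, with limits stated separately for transaminases and for bilirubin.
2. Bring the Section 7.1 restart rule for non-hematologic DLT and the Section 7.5 laboratory-abnormality bullet into line with that rule, or state that they do not apply to liver tests.
3. Add one sentence saying which text governs nivolumab dosing when the table and the algorithm differ.
4. Correct the Section 7.1 cross-reference for nivolumab from 7.3 to 7.5, and the table of contents with it.

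Which limits and conditions to adopt is the sponsor's clinical choice; this review takes no view. The cost is a wording amendment to one table, one footnote and a few sentences, with no change to sample size or planned analyses.

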
*Including CHF, LV systolic dysfunction, Myocarditis, CPK, and troponin
 
**Patients with evidence of myositis without myocarditis may be treated according as “other event”
 
Note: The optimal treatment regimen for immune mediated myocarditis has not been established. Since this toxicity has caused patient deaths, an aggressive approach is recommended.
	

All Other Events	Management/Next Dose for Nivolumab
$\leq$ Grade 1	No change in dose.
Grade 2	Hold until $\leq$ Grade 1 OR baseline (exceptions as noted below).
Grade 3	Hold until $\leq$ Grade 1 OR baseline and patient no longer on steroid treatment if initiated (exceptions as noted below). Permanently discontinue for events with a high likelihood of morbidity or mortality with recurrent events.
Grade 4	Off protocol therapy.
Recommended management: As clinically indicated	

- Any Grade 2 drug-related uveitis or eye pain or blurred vision that does not respond to topical therapy and does not improve to Grade 1 severity within the re-treatment period OR requires systemic treatment should go off protocol treatment
- Any Grade 3 or 4 drug-related laboratory abnormality or electrolyte abnormality, that can be managed independently from underlying organ pathology with electrolyte replacement, hormone replacement, insulin or that does not require treatment **does not** require discontinuation.
- Any AE, laboratory abnormality, or intercurrent illness which, in the judgment of the investigator, presents a substantial clinical risk to the subject with continued study drug dosing should go off protocol treatment.

Skin Rash and Oral Lesions	Management/Next Dose for Nivolumab
≤ Grade 1	No change in dose*.
Grade 2	Hold* until 1≤ Grade resolved. Resume at same dose level.
Grade 3	Hold* until ≤ Grade 1. Resume at same level at investigator discretion
Grade 4	Off protocol therapy.

\*Patients with purpuric or bullous lesions must be evaluated for vasculitis, Steven-Johnson syndrome, toxic epidermal necrolysis (TEN), and autoimmune bullous disease including oral lesions of bullous pemphigus/pemphigoid. Pruritus may occur with or without skin rash and should be treated symptomatically if there is no associated liver or GI toxicity. Note skin rash typically occurs early and may be followed by additional events particularly during steroids tapering.

Recommended management: AE management guidelines

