Grade 3	Continue at same dose level if asymptomatic at investigator discretion. Patients should have imaging study when clinically indicated (grade 3 symptomatic pancreatitis) before resuming treatment. Patients who develop diabetes mellitus should be taken off treatment.
Grade 4	Hold until grade 2. Resume at same dose level if asymptomatic. Patients who are symptomatic should have imaging study prior to resuming treatment and when clinically indicated. Patients who develop grade 4 symptomatic pancreatitis or diabetes mellitus should be taken off treatment.
Patients may develop symptomatic and radiologic evidence of pancreatitis as well as diabetes mellitus and diabetic ketoacidosis (DKA). Lipase elevation may occur during the period of steroid withdrawal and with other immune-mediated events or associated with colitis, hepatitis, and patients who have asymptomatic lipase elevation typically have self-limited course and may be retreated.	

For treatment management of symptomatic pancreatitis, please follow the Hepatic AE Management Algorithm.

Pneumonitis	Management/Next Dose for Nivolumab
≤ Grade 1	Hold dose pending evaluation and resolution to baseline including baseline pO 2 . Resume no change in dose after pulmonary and/or infectious disease (ID) consultation excludes lymphocytic pneumonitis.
Grade 2	Hold dose pending evaluation. Resume no change in dose after pulmonary and/or ID consultation excludes ipilimumab and associated lymphocytic pneumonitis as the cause of the pneumonitis. Off study if steroids are required.
Grade 3	Hold dose pending evaluation. Resume no change in dose after pulmonary and/or ID consultation excludes ipilimumab and associated lymphocytic pneumonitis as the cause of the pneumonitis. Off protocol treatment.
Grade 4	Off protocol therapy.
Distinguishing inflammatory pneumonitis is often a diagnosis of exclusion for patients who do not respond to antibiotics and have no causal organism identified, including influenza. Most patients with respiratory failure or hypoxia will be treated with steroids. Bronchoscopy may be required and analysis of lavage fluid for lymphocytic predominance may be helpful. Patients with new lung nodules should be evaluated for sarcoid like granuloma. Please consider recommending seasonal influenza killed vaccine for all patients.	
Recommended management: See Pulmonary AE Management Algorithm	

Other GI Nausea/Vomiting	Management/Next Dose for Nivolumab

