Prior to starting corticosteroids or hormone replacement for any reason, appropriate

endocrine testing including cortisol, Cortrosyn® adrenocorticotropic hormone (ACTH), thyroid stimulating hormone (TSH), and thyroxine (T4) must be obtained to document baseline.

Please note that in some cases the treatment algorithms recommend steroids if symptoms do not resolve in 7 days. However, this recommendation is not meant to delay steroid treatment at any time it is clinically indicated.

Any patient started on corticosteroids initially, who is determined to not require steroid treatment for an autoimmune AE, may resume therapy after a 2-week observation period without further symptoms at the discretion of the PI or investigator.

Any patient requiring high dose steroids (any dose greater than the equivalent to 20 mg prednisone) will be considered to have experienced a DLT and will be taken off nivolumab. These patients will be allowed to continue receiving decitabine and venetoclax on study.

Patients requiring high dose steroid treatment for autoimmune or inflammatory events should go off study treatment except for a short course of tapering steroids for infusion reaction, skin rash or endocrine events.

Patients with grade 3 thyroiditis and skin rash may continue therapy as for grade 2 events with resolution and stable replacement treatment.

Patients with thyroiditis or hypopituitarism who are stable as above may be restarted with replacement hormones including thyroid hormone and physiologic doses of corticosteroids.

Please note that grading and for hypophysitis with symptoms of headache, visual or neurologic changes or radiologic evidence of pituitary enlargement and other CNS events such as aseptic meningitis or encephalitis should be considered grade 3 events.

Patients may be dose-delayed for evaluation and restarted depending on results.

Any patient started on corticosteroids initially who is determined to not require steroid treatment for an autoimmune adverse event may resume therapy after a 2-week observation period without further symptoms at the discretion of the PI or investigator.

If doses of nivolumab are missed/delayed other than reasons for toxicity, they may be given +2 days of scheduled dose.

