# Pulmonary Adverse Event Management Algorithm

[figure not shown]
Rule out non-inflammatory causes. If non-inflammatory cause, treat accordingly and continue I-O therapy. Evaluate with imaging and pulmonary consultation.

Patients on IV steroids may be switched to an equivalent dose of oral corticosteroids (e.g. prednisone) at start of tapering or earlier, once sustained clinical improvement is observed. Lower bioavailability of oral corticosteroids should be taken into account when switching to the equivalent dose of oral corticosteroids.

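### Section 7.5 pneumonitis table: the grade 2 and 3 resume tests name ipilimumab instead of nivolumab, and the grade 3 instruction to stop has no stated condition

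*Combined protocol and SAP*

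**What the plan says.** The pneumonitis table in Section 7.5 is headed as guidance on the next dose of nivolumab. Its cells run as follows.

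- **Grade 1 or less.** Hold until evaluated and back to baseline. Then: "Resume no change in dose after pulmonary and/or infectious disease (ID) consultation excludes lymphocytic pneumonitis". No drug is named.
- **Grade 2.** Hold; the resume test is worded to exclude ipilimumab and lymphocytic pneumonitis. The cell ends with a stated stopping condition: "Off study if steroids are required".
- **Grade 3.** Hold, then: "Resume no change in dose after pulmonary and/or ID consultation excludes ipilimumab and associated lymphocytic pneumonitis as the cause of the pneumonitis. Off protocol treatment".
- At **grade 4** the patient leaves protocol therapy.

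A note under the table says that inflammatory pneumonitis is often diagnosed by exclusion, and that steroids will be given to most patients with hypoxia or respiratory failure. It points to the pulmonary algorithm in Appendix E. The readable text of that algorithm says: "If non-inflammatory cause, treat accordingly and continue I-O therapy. Evaluate with imaging and pulmonary consultation". The rest is a figure that is not reproduced in the public document.

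The regimen in Section 6.1 is venetoclax, decitabine and nivolumab. Outside this table, ipilimumab appears only in Section 2.2.1, as the partner drug in a labelled nivolumab dosing scheme.

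**The concern.** This is an operative safety rule that a site would consult with a sick patient on study.

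The test for restarting nivolumab does not name nivolumab, although the nivolumab risk list in Section 10.1.1 includes pneumonitis. It names a drug that nobody receives as study treatment.

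The grade 3 cell then gives two instructions without saying how they relate. One site could take the closing words as an absolute stop. Another could take them to mean stop unless the exclusion test is met. The same patient would come off treatment at the first site and could restart at the second. What is at stake is consistent safety management and continuation of dosing in a three-drug combination that Section 2.5.4 describes as novel.

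**Working it through.** No arithmetic beyond a count applies, so the check sets the texts side by side.

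**Step 1: the drug named.** Sections 6.1 and 9.1 list nivolumab, decitabine and venetoclax, and Section 6.3.2 speaks of three study drugs. Ipilimumab is not among them. Excluding ipilimumab as the cause is therefore automatic on study. The lymphocytic pneumonitis part of the test still has effect, and it is the whole of the grade 1 test. That nivolumab was the intended drug is an inference, supported by the section title and the column heading.

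**Step 2: the two branches at grade 3.** The resume branch has a condition, namely that consultation excludes the named causes. The stop branch has none: no 'if' and no 'otherwise' joins the two sentences.

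**Step 3: comparison with the other tables.** The grade 3 instructions in the 14 toxicity tables of Section 7.5 fall into four groups:

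| Grade 3 instruction | Tables | Count |
|---|---|---|
| Continue or resume, plus a stop with a stated condition | all other events, liver, diarrhea/colitis, pancreatitis, nausea/vomiting, cardiac | 6 |
| Resume only | skin, fatigue, endocrine, renal, infusion reaction, fever | 6 |
| Off only | neurologic | 1 |
| Resume, plus a stop with no stated condition | pneumonitis | 1 |

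6 + 6 + 1 + 1 = 14. Thirteen tables have their own grade 3 row; the cardiac table covers grade 3 in its rows for grade 2 and above. The liver and diarrhea/colitis cells are the cleanest comparators: both stop treatment if the event persists or steroids are needed. The cardiac table also separates its branches. For suspected myocarditis it says "May resume therapy if there is a return to baseline and myocarditis is excluded or considered unlikely"; confirmed myocarditis goes off protocol therapy.

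**Step 4: whether another rule settles the cell.**

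- Section 7.5 says: "Nivolumab must be withheld for drug-related toxicities and severe or life-threatening AES". This requires a hold, which the cell already orders, and does not decide between restarting and stopping.
- An event that in the investigator's judgment "presents a substantial clinical risk to the subject with continued study drug dosing should go off protocol treatment". This catches serious cases case by case, but does not say which half of the cell governs.
- "Patients requiring high dose steroid treatment for autoimmune or inflammatory events should go off study treatment except for a short course of tapering steroids". The exceptions are infusion reaction, skin rash and endocrine events, so pneumonitis is caught, but only when steroids are high dose.
- Section 7.5 also lets a patient who started steroids, and proved not to need them for an autoimmune event, resume after two symptom-free weeks of observation. This too covers only part of the group.
- Section 7.1 allows restart after a non-hematologic DLT once the event is grade 1 or less or at baseline, and refers the reader to the nivolumab-specific rules for that drug.
- The readable Appendix E text continues therapy for a non-inflammatory cause. That supports 'otherwise off' as the intent and sits badly with an absolute stop, but it does not correct the cell.

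None of the readable rules reconciles the two instructions.

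**The case against.** The strongest reply is that little turns on this in practice. A clinician will see that nivolumab was meant, and lymphocytic pneumonitis has to be excluded in any case. By the table's own note, most patients with hypoxia or respiratory failure will receive steroids, so the group not caught by a steroid rule is narrow. Section 7.5 also recommends consulting the study PI or drug monitor, and the Appendix E figure may state the rule clearly. All of this stands, and it is why the point is minor. It does not make the two sentences in the cell agree.

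Three stronger readings are tempting and are not supported.

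- A reader might infer that the restart test is empty because nobody receives ipilimumab. It is not: the lymphocytic pneumonitis part remains.
- A reader might infer that grade 3 patients on low-dose steroids could simply restart, while grade 2 patients on any steroid must stop. Restart at grade 3 still requires the exclusion, and the two-week observation rule covers the most natural such case, though not every low-dose use.
- A reader might infer that the grade 3 cell should already contain a steroid stop or a recovery threshold. Their absence is a clinical choice open to the sponsor, not part of the error.

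The cardiac comparison is also imperfect. A separate bullet in Section 7.5 permanently discontinues nivolumab for treatment-related grade 3 or 4 cardiac dysfunction, so the reader has to combine two texts there as well. The liver and diarrhea/colitis cells carry the comparison without it.

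**Conclusion.** The table is wrong as written in two respects: the drug named in the grade 2 and grade 3 resume tests, and the missing condition on the grade 3 stop. The extent is two cells in one of 14 tables. Section 10.1.1 places pneumonitis of any grade in its less-likely column (20% or below). No grade 3 rate is given, so no patient count is claimed; the affected group is expected to be small.

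The wording errors themselves are certain. Their practical consequence is less so, because it depends on an Appendix E figure that is not shown and on how sites have read the cell. DLT classification under Section 6.3 rests on grade, drug-relatedness and steroid use, and does not depend on this cell. The sample size and the response rule in Section 9.1 are likewise untouched. Severity is minor.

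**What to change.** In the grade 2 and grade 3 cells, replace the phrase naming ipilimumab with *nivolumab-related (immune-mediated) or lymphocytic pneumonitis*. End the grade 3 cell with *; otherwise, off protocol treatment.* Keep the grade 2 steroid sentence as it is. Check the result against the full pulmonary algorithm in Appendix E.

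As an option, separate from the correction, the sponsor may consider aligning grade 3 with the grade 2 steroid stop and with the Section 7.1 recovery requirement (grade 1 or less, or baseline). Any such addition should be reconciled with Sections 6.3, 7.5 and 7.6, under which a patient needing high-dose steroids stops nivolumab but may continue decitabine and venetoclax.

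The cost is an edit to two cells, with no change to design or sample size. The downside is that a few grade 3 patients may be handled differently from how a site would have read the current cell.
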